## 1.1.4 Pembrolizumab Clinical Trial Data

### 1.1.4.1 Pembrolizumab

Pembrolizumab (Keytruda®; previously known as SCH 900475/MK3475) is a potent and highly selective humanized monoclonal antibody of the IgG4/kappa isotype designed to directly block the interaction between PD-1 and its ligands, PD-L1 and PD-L2.

### 1.1.4.2 Clinical Trial Data

Pembrolizumab has also showed excellent activity in the second-line setting for advanced NSCLC and was granted accelerated drug approval with the Food and Drug Administration (FDA) following the results from the expanded phase 1 study, KEYNOTE-001 (57), and the most recent data from KEYNOTE-010 (58). KEYNOTE-001 included 495 patients with advanced NSCLC, with both squamous and non-squamous histology. Of the patients treated, 81% had received at least one-line of prior treatment. The dose expansion assessed multiple doses. After a median follow-up of 10.9 months, the median OS was 12.0 months for all patients, and 10.4 months in previously treated patients. The median PFS was 3.7 months for all patients,

and 3.0 months in previously treated patients. ORR was 19.4% in all patients, and 18.0% in previously treated patients. The median duration of response was again more impressive than the PFS at 12.5 months (range: 1.0–23.3 months). When stratified for PD-L1 expression (Table 1), they showed that tumour proportionate score (TPS) of  $\geq 50\%$  was predictive of better response, PFS and OS. Interestingly, the response rates in smokers were twice as high when compared with non-smokers and there was little difference between squamous and non-squamous histological subtypes (57).

KEYNOTE-010 was a head-to-head assessment of pembrolizumab (2 mg/kg and 10 mg/kg) with docetaxel in the second-line setting. The median OS was again in favour of pembrolizumab (2 mg/kg: 10.4 months, HR=0.71, *P-value*=0.0008; and 10 mg/kg: 12.7 months, HR=0.61, *P-value*<0.0001) over docetaxel (8.5 months). The median PFS was 3.9–4.0 months, with no difference across the arms. When stratified for PD-L1 expression, PD-L1 positive patients (TPS  $\geq 50\%$ ), the median OS was again in favour of pembrolizumab (2 mg/kg: 14.9 months, HR=0.54, *P-value*=0.0002; and 10 mg/kg: 17.3 months, HR=0.50, *P-value*<0.0001) over docetaxel (8.2 months). Likewise, for this patient population, the median PFS was again in favour of pembrolizumab (2 mg/kg: 5.0 months, HR=0.59, *P-value*=0.0001; and 10 mg/kg: 5.2 months, HR=0.59, *P-value*<0.0001) over docetaxel (4.1 months). The response rate was ~30% in PD-L1 positive patients receiving pembrolizumab versus 8% receiving docetaxel, and in all patients, this was 18% versus 9%, respectively (58).

Recent data supports the use of PD-1 inhibition in treatment-naïve advanced NSCLC patients. KEYNOTE-024 compared pembrolizumab against investigators choice of platinum-based doublet chemotherapy, enriched for PD-L1 positive patients (TPS  $\geq 50\%$ ). This shown a significant difference in median PFS favouring pembrolizumab (10.3 versus 6.0 months), and a significant difference in OS, again in favour of pembrolizumab (1-year OS of 80.2% versus 72.4%). The response rate was significantly higher in the pembrolizumab arm compared chemotherapy (44.8% versus 27.8%). The toxicity data did not reveal any new adverse events that were not already known about pembrolizumab, and again it was in support of pembrolizumab over platinum-based doublet chemotherapy (59). KEYNOTE-042 is of a similar design in an Asian population, but stratified patients into two PD-L1 positive groups: low expression (1–49%) and high expression ( $\geq 50\%$ ; NCT02220894), the results of which are still awaited.

Adverse events of grade 3–5 occurred in 13–16% of the patients receiving pembrolizumab, and 35% of the patients receiving docetaxel. Treatment discontinuation due to treatment-related adverse events was seen in 4–5% of patients receiving pembrolizumab compared with 10% receiving docetaxel. Treatment-related deaths occurred in three patients in the 2 mg/kg arm (2 with pneumonitis, and 1 with pneumonia), 3 patients in the 10 mg/kg arm (1 each with myocardial infarction, pneumonia, pneumonitis), and 5 patients on docetaxel (1 each with acute cardiac failure, dehydration, febrile neutropenia, interstitial lung disease, and respiratory tract infection). Immune-related adverse events occurred in ~20% of patients receiving pembrolizumab, with the most common being hyperthyroidism (4–6%), hypothyroidism (8%), and

pneumonitis (4-5%). The immune-related adverse events of grade 3-5 severity occurring in  $\geq 1\%$  of patients were pneumonitis (2%) and severe skin reactions (1-2%) (58).

These data have resulted in pembrolizumab being granted breakthrough therapy designation with the FDA for patients with NSCLC whose cancers have progressed on or after platinum-containing chemotherapy, as well as targeted agents in those with *EGFR* mutations and *ALK* gene rearrangements (60).

KEYNOTE-001 also validated the PD-1 biomarker using the anti-PD-1 antibody clone 22C3 (Merck) and immunohistochemistry. Tumour slides were stained and scored for neoplastic membranous staining (i.e. the TPS) as <1%, 1-49%, or >50%. Using receiver operator characteristic curve analysis they found that a PD-L1 score of >50% (strong) was the best predictor of efficacy of pembrolizumab, with a response rate of 45.2% (95%CI: 33.5 – 57.3) and a median PFS of 6.3 months. The media OS has not yet been reached. The response rates in patients who scored PD-L1 1-49% was 16.5% (95%CI: 9.9 – 25.1) and in those who scored PD-L1 <1% was 10.7% (95%CI: 2.3 – 28.2). As responses were seen across all PD-L1 scores, this clinical trial will explore the combination of pembrolizumab and lung SBRT unenriched for PD-L1 strong (57).

## 1.2 Rationale for the Trial

The abscopal effect refers to a rare phenomenon of tumour regression at a site distant from the primary site of radiotherapy (61). Radiotherapy has been shown to induce abscopal effects in several types of cancer, including melanoma, lymphoma, renal-cell carcinoma and NSCLC (62-65). The effect is attributed to activation of the systemic immune response. Radiation-induced inflammation is known to increase antigen presentation, subsequent tumour recognition, and can ultimately, enhance the tumour-directed immune response (66). This effect may be more pronounced in response to ablative rather than conventional dosage or fractionation schedules (67). More recently, the abscopal effect has been described in the context of patients receiving immunotherapy concurrently with radiotherapy. Formenti *et al* described a case of abscopal response in a patient with advanced NSCLC who received palliative hepatic radiotherapy while on ipilimumab. The response was seen 2.5 months following radiotherapy (68). Experimental data from multiple cancer models have provided sufficient evidence to propose a paradigm shift, whereby some of the effects of radiation are recognised as contributing to systemic antitumor immunity. Therefore, the traditional palliative role of radiotherapy in metastatic disease is evolving into that of a powerful adjuvant for immunotherapy. This combination strategy adds to the current anticancer arsenal and offers opportunities to harness the immune system to extend survival, even among metastatic and heavily pretreated cancer patients (36). Combination trials of immunotherapy and SBRT are required to explore the potential for radiation enhancing the effects of immunotherapy with the aim of improving outcomes for patients with NSCLC (36). The initial step is to assess the tolerability and safety of immunotherapy with SBRT. This clinical trial protocol will look at the safety and tolerability of pembrolizumab, an anti-PD-1 monoclonal antibody, given in combination with lung SBRT in patients with advanced NSCLC.

## **2 STUDY OBJECTIVES & ENDPOINTS**

---

### **2.1 Study Objectives & Hypothesis**

#### **2.1.1 Primary Objective & Hypothesis**

- Objective: To assess the safety and tolerability of lung SBRT with pembrolizumab and to determine the RP2D of lung SBRT to be used in combination with pembrolizumab.
- Hypothesis: Lung SBRT can be safely administered in combination with pembrolizumab without significant DLTs.

#### **2.1.2 Secondary Objectives**

- To describe the safety profile of lung SBRT in combination with pembrolizumab.
- To assess clinical benefit with overall responses rate (ORR) and disease control rate (DCR).
- To assess responses rates in squamous versus non-squamous histological subtypes of NSCLC.
- To assess response rates in relation to tumour PD-1/PD-L1 expression.
- To assess progression free survival (PFS) and overall survival (OS).

#### **2.1.3 Exploratory Objectives**

- To identify biomarkers that correlate with immunological response to therapy.
- To analyse peripheral blood samples for ctDNA.

## **2.2 Study Endpoints**

### **2.2.1 Primary Endpoint**

- To establish the MTD and RP2D of lung SBRT that can be safely combined with pembrolizumab.

### **2.2.2 Secondary Endpoints**

- To assess the rates of acute toxicity (defined as up to 12 weeks after the last fraction of stereotactic radiotherapy) using CTC AE v4.0.
- To assess the rates of late toxicity (defined as from 12 weeks after last fraction of lung SBRT until 28 days after the last dose of pembrolizumab) using CTCAE version 4.0.
- To calculate the ORR and DCR using RECIST v1.1 & irRC.
- To calculate the ORR and DCR in squamous versus non-squamous histological subtype using RECIST v1.1 & irRC.
- To assess the frequency of PD-1/PD-L1 expression distribution in responders and non-responders.
- To measure the PFS and OS at 6 and 12 months.

### 2.2.3 Exploratory Endpoints

- To characterise TILs and tumour antigens in the tumour biopsies. These immunohistochemistry analyses will include, but not necessarily be limited to, the following markers: CD4, CD8, FOXP3, PD-1, PD-L1, and PD-L2.
- To assess for levels of ctDNA pre- and post- SBRT.

### 3 STUDY DESIGN

---

#### 3.1 Summary of Study Design

This is a single centre non-randomised open label phase 1 trial of lung SBRT to part of a lung lesion in patients with advanced NSCLC in combination with pembrolizumab. This study will recruit up to 24 patients whose lung cancer has progressed beyond one line of palliative chemotherapy, and an EGFR or ALK inhibitor if an *EGFR* driver mutation or *ALK* gene rearrangement is present, respectively, and now requires further palliative systemic treatment.

#### 3.2 Treatment Regimen

The study will be conducted in two parts; an initial lung SBRT dose escalation phase (Part A), followed by a lung SBRT dose expansion cohort (Part B). The dose escalation phase is based on a 3+3 design such that patients will be treated in cohorts of 3-6 patients. A maximum of 12 patients will be allocated to one of two doses of lung SBRT in combination with pembrolizumab to determine the MTD, DLTs and RP2D. If there is more than one DLT in cohort 1, this treatment combination will be deemed as being unacceptable, and it would lead to termination of the study. Note, there is no de-escalation in cohort 1. During the dose expansion cohort, 12 patients will have lung SBRT dosed at the RP2D determined during the dose escalation phase in combination with pembrolizumab to obtain additional safety and response data. Maintenance pembrolizumab will continue until disease progression, unacceptable toxicities, the patient withdraws consent to the trial, or the patient has completed 24 months of treatment. A maximum of 24 patients will be treated in the study.

All patients will receive pembrolizumab on cycle (C) 1 day (D) 1, in Part A and B of the study. All patients will receive lung SBRT on C1D15, C1D17, and C1D19 as per lung SBRT protocol (See Appendix 3). Although C1D1 can occur +/- 3 days, C1D15, C1D17, and C1D19, must be scheduled for a Monday, Wednesday and Friday, respectively. Patients in part A will receive lung SBRT dosed at 30 Gy in 3# in cohort 1, or 54 Gy in 3# in cohort 2. Patients in Part B will receive the RP2D of lung SBRT, determined in Part A. All patients in Part A and Part B will receive pembrolizumab dosed at 200 mg every 3 weeks, until disease progression, unacceptable toxicities, the patient withdraws consent from the trial, or the patient has completed 24 months of treatment.

In the dose escalation phase, a minimum of 3 patients will be required per dose level being assessed. A minimum gap of 1 week will be left between the treatment of the first and the second, and between the second and the third patients with the combination of pembrolizumab and lung SBRT to mitigate against multiple patients suffering from acute toxicity. The DLT period for this study is 12 weeks from the last dose of lung SBRT (i.e. at C6D1). The dose escalation will be considered by the Safety Review Committee (SRC) once the 3rd or 6th patient in the cohort has completed the DLT period. If no DLT is observed at a dose level,

then lung SBRT will be dose escalated to the next dosing level (see Table 1). If 1 out of 3 patients experience a DLT, then the cohort will be expanded to 6 patients. If 1 in 6 patients experience a DLT, then the dose will be escalated to the next dosing level. However, if  $\geq 2$  in 6 patients experience a DLT then the maximum administered dose (MAD) will have been reached, and the RP2D will be the previous dosing level that will be used for the dose expansion cohorts. If the MAD is seen at dose level 1 then the study will be terminated. While waiting for 3 or 6 patients to complete the DLT period, no additional patients will be recruited. Further patients can only be recruited after the SRC has reviewed the toxicity data for the cohort and taken a decision to dose escalate to the next cohort or expand the current cohort to 6 patients.

Once the MTD has been determined the trial enters the dose expansion phase (unless the MTD is dose level 1). Here, 12 patients will be treated with the RP2D of SBRT combined with pembrolizumab.

If there is ongoing clinical benefit at 24 months, the CI/PI will need to discuss with the sponsor and MSD, on a case by case basis for the continuation of pembrolizumab.

**Table 1:** Lung SBRT dose levels and pembrolizumab dosing during the dose escalation and dose expansion phase.

Dose Level	Pembrolizumab Dose	Lung SBRT to part of a lung lesion
1	200 mg i.v. over 30 minutes, every 3 weeks	30 Gy in 3# (Monday, Wednesday, Friday)
2	200 mg i.v. over 30 minutes, every 3 weeks	54 Gy in 3# (Monday, Wednesday, Friday)
Dose expansion	200 mg i.v. over 30 minutes, every 3 weeks	RP2D

SBRT: Stereotactic Ablative Body Radiotherapy; Gy: Gray; i.v.: intravenous; mg: milligrams;  
RP2D: Recommended Phase 2 Dose; #: fraction.

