## **Non-Haematologic:**

Any NCI CTCAE  $\geq 3$  grade non-haematological toxicity that is definitely, probably or possibly related to the combination of pembrolizumab and lung SBRT including the following:

[figure not shown]
- Increased MRC dyspnoea score  $> 2$  grades from baseline and/or acute dyspnoea grade  $\geq 4$  (or CTCAE dyspnoea grade  $\geq 3$ ) persisting for  $> 7$  days (including weekend).
- Pneumonitis/pulmonary infiltrates grade  $\geq 3$  persisting for  $> 7$  days (including weekend).
- Oesophagitis grade  $\geq 3$  persisting for  $> 7$  days (including weekend).
- Toxicity leading to interruption of radiotherapy for  $> 7$  days (including weekend).

Escalation to the next dose level will not proceed until the following criteria are satisfied by the SRC:

- If 0 out of 3 patients experience a DLT, escalation to the next dose level can proceed.
- If 1 out of 3 patients experiences a DLT, a further 3 patients will be recruited at that dose level.
  - If 1 out of 6 patients experiences a DLT, then escalation to the next dose level can proceed.
  - If  $\geq 2$  out of 6 patients experience a DLT, the MAD will have been reached. The RP2D will be the dose level prior to when the DLTs were observed or dose level 2 if no DLTs were observed.  
All patients in the expansion cohort will have lung SBRT dosed at the RP2D (see Figure 1).
- If 2/3 patients experience a DLT then the MAD will have been reached and the expansion cohort phase will begin at the previous dose level unless this occurs at dose level 1.
- If dose level 1 is not tolerated due to DLTs, the expansion cohort will not go ahead and the trial will be terminated.

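### One sentence in Section 3.2 bars Part B at 30 Gy when 54 Gy fails, although the other dose-finding rules open it; MTD there is almost certainly a slip for MAD

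*Combined protocol and SAP*

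**What the plan says.** Part A is a 3+3 escalation over two SBRT dose levels, 30 Gy and 54 Gy in 3 fractions (Section 3.2, Table 1). Part B then adds 12 patients: "12 patients will have lung SBRT dosed at the RP2D determined during the dose escalation phase".

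In Section 3.2, two or more DLTs in six patients means the MAD has been reached, and "the RP2D will be the previous dosing level that will be used for the dose expansion cohorts". The stop at the bottom level is stated in terms of the MAD: "If the MAD is seen at dose level 1 then the study will be terminated". The next paragraph then reads: "Once the MTD has been determined the trial enters the dose expansion phase (unless the MTD is dose level 1"), the bracket closing there.

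Section 3.2.1 repeats the escalation rules. For two DLTs in three patients, "the expansion cohort phase will begin at the previous dose level unless this occurs at dose level 1". It cancels Part B under one condition: "If dose level 1 is not tolerated due to DLTs, the expansion cohort will not go ahead and the trial will be terminated".

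The protocol does not formally define MTD. The Trial Summary, under both Treatment Groups and Treatment / Main Study Procedures, uses it for the dose given in Part B.

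**The concern.** When level 1 passes and level 2 fails, the previous level can only be level 1, because Table 1 has just two levels. Level 1 is then the RP2D, the dose for Part B and, as the Trial Summary uses the term, the MTD. One sentence of Section 3.2 opens Part B at 30 Gy and another, in the next paragraph, forbids it.

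The MTD and RP2D are the primary endpoint (Section 2.2.1). Section 8.2 gives the purpose of the 12 expansion patients as learning more about the toxicity of the dose that may go to phase II. The sentence therefore decides whether that information is collected in the very case where the higher dose has proved too toxic. The realistic harm is a dispute or a late amendment at that moment.

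**Working it through.** **The plan's own figure.** Two levels of 3 to 6 patients give 2 × 3 = 6 to 2 × 6 = 12 in Part A; adding 12 for Part B gives at most 24, as Sections 3.2 and 8.2 state. The conflict does not change this maximum.

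**Tracing the branches.**

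| Outcome of Part A | Other rules in 3.2, 3.2.1 and 3.5.1 | Sentence as written | Sentence with MAD |
|---|---|---|---|
| Level 1 has 2 or more DLTs | Stop, no Part B | No tolerated dose, so the exception does not describe this case | Stop, no Part B |
| Level 1 passes, level 2 has 2 or more DLTs | Part B at 30 Gy; 18 to 24 patients in all | No Part B; 6 to 12 patients in all | Part B at 30 Gy; 18 to 24 in all |
| Level 1 passes, level 2 has at most 1 DLT | Part B at 54 Gy; 18 to 24 in all | Part B at 54 Gy | Part B at 54 Gy |

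As written, Part B could open only at level 2, so the previous-level rules in Sections 3.2 and 3.2.1 could never operate. With MAD in the brackets, all three branches agree with the other rules. (The third row takes 1 of 6 at level 2 as a pass; see the last paragraph.)

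**Chance of reaching the middle branch.** The documents give no DLT rate, so every rate p below is an assumption. For one level:

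- P(0/3) = (1 − p)³
- P(1/6) = 3p(1 − p)² × (1 − p)³ = 3p(1 − p)⁵
- P(MAD) = 1 − P(0/3) − P(1/6)

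| p | P(0/3) | P(1/6) | P(MAD) |
|---|---|---|---|
| 5% | 0.857 | 0.116 | 0.027 |
| 10% | 0.729 | 0.177 | 0.094 |
| 20% | 0.512 | 0.197 | 0.291 |
| 30% | 0.343 | 0.151 | 0.506 |

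Once level 2 is open, the last column is the chance of meeting the conflict. As a share of all trials started it is P(level 1 passes) × P(MAD at level 2), where P(level 1 passes) = 1 − P(MAD) at level 1:

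- 5% / 5%: 0.973 × 0.027 = 0.026
- 10% / 10%: 0.906 × 0.094 = 0.085
- 20% / 20%: 0.709 × 0.291 = 0.206
- 10% / 20%: 0.906 × 0.291 = 0.264
- 10% / 30%: 0.906 × 0.506 = 0.458

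**What is lost.** Without Part B, 30 Gy has been tested in 3 or 6 patients; with it, in 3 + 12 = 15 or 6 + 12 = 18. Section 8.1.1 reports the DLT proportion with an exact 95% interval. With no DLT in 3 patients the upper limit is 71%; with none in 15 it is 22%. With 1 in 6 it is 64%; with 1 in 18 it is 27%. These pairs assume that Part B is pooled with Part A, which Section 8.1.1 does not say, and that Part B adds no DLTs.

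**A related gap.** For one DLT in six, Section 3.2 says "If 1 in 6 patients experience a DLT, then the dose will be escalated to the next dosing level". Above level 2 there is no next level, and Section 3.2.1 names level 2 as the RP2D only when there are no DLTs. Both sections treat 1 of 6 as a pass, and the standard 3+3 design named in Section 8.2 implies 54 Gy. This is a missing sentence rather than a conflict, and the branch probabilities above do not include it.

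**The case against.** The strongest reply is that the intended rule is already plain. Sections 3.2, 3.2.1 and 3.5.1 all tie termination to two or more DLTs at level 1, and one parenthesis stands against them, so a reader can resolve the slip from the same page. Nobody is dosed automatically either: "Further patients can only be recruited after the SRC has reviewed the toxicity data for the cohort", and Section 10.9 gives the committee the escalation decisions. Read literally, the sentence treats fewer patients and exposes no one to a higher dose. The percentages rest on assumed rates and measure how often level 2 fails, not how often a dispute follows. Section 1.1.3 also cites supportive safety data for 54 Gy in peripheral lesions, though not with pembrolizumab.

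Most of this is correct, and it limits the point to a wording correction rather than a safety alarm. It does not remove the contradiction, which sits in an operative decision rule.

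Three caveats stand. That MAD was meant is an inference, although a well-supported one. Section 3.2.1 refers to Figure 1, which is not shown in the copy reviewed; its caption describes study events and doses, but the figure might restate the rule. Even a correct figure would leave the conflicting sentence in the text. Finally, the Trial Summary says that DLTs at level 1 end the study without giving a count, which is looser than Sections 3.2 and 3.5.1. That does not bar Part B at a level 1 free of DLTs, but it could be read to exclude one that passed with 1 of 6.

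**Conclusion.** The concern holds. One sentence in Section 3.2 contradicts the rule in the paragraph before it, and Section 3.2.1, in exactly one branch: level 1 tolerated, level 2 not. In that branch Part B has 12 patients at 30 Gy under the other rules and none under this sentence. Under the assumed DLT rates, the branch arises in about 3% to 46% of trials started, depending mainly on the level 2 rate. The conclusion rests on reading MTD as the Part B dose, as the Trial Summary does and as is usual in a 3+3 design. The choice of a 3+3 design is not in question. The correction should be made because the sentence governs the primary endpoint's supporting data and costs almost nothing to put right.

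**What to change.** In the bracketed exception of the Section 3.2 sentence, replace MTD by MAD. The first MTD in that sentence is correct and stays.

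As a clarification, add to Section 3.2.1 a statement of the level 2 outcomes: DLTs in 0 of 3 or 1 of 6 patients make level 2 the MTD and RP2D; DLTs in two or more patients make level 1 the MTD and RP2D, and Part B opens at 30 Gy. Check that Figure 1 agrees, and put the DLT count from Section 3.5.1 into the Trial Summary's termination sentence.

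Make these changes before level 2 is evaluated. They are wording only: no extra patients, visits or data.
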